#### **8.6 MMTT Description**

The 4-hour Mixed Meal Tolerance Test (MMTT) will be performed as a measure of beta cell function at multiple visits during the study. The MMTT will be performed in the morning after an overnight fast, with no food or drink (with the exception of water). At the outset, a mixed meal, consisting of High Protein Boost will be administered. Blood samples for C-peptide and glucose will be collected at the following timepoints (in minutes, relative to administration of the mixed-meal): - 10, 0, 15, 30, and then at 30 minute-intervals until the last time point of 240 minutes. An MMTT protocol is provided to the investigational centers that describes the procedures for performing the MMTT, including preparation and sampling times.

### **8.7 Prior and Concomitant Therapy and Insulin Usage**

Study participants will continue all regularly prescribed medications, except for any diabetes medications other than insulin. For subjects who are already on diabetes medications and for whom it is clinically appropriate to discontinue, they will do a wash off period of at least 3 weeks prior to initiation of leukapheresis. The introduction of systemic immunosuppressive agents, however, will constitute grounds for withdrawal from the study. However, topical creams (e.g., steroidal) and inhaled steroids without large systemic absorption are allowed.

Insulin usage will be recorded, using the insulin log, 3-7 days, each day, prior to visit separately from prior/concomitant medication therapies. Insulin usage will include description of the daily total dose and regimen. Additional instructions for use are provided on the insulin log.

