### 5.6.1 Stopping Rules

Subjects will be clinically evaluated for evidence of toxicity from  $\geq$  grade 3 toxicity as determined by CTCAE which is unmanageable, unexpected and (possibly, probably or definitely) related, and attributable to protocol therapy. Termination of enrollment would be considered with 2 dose limiting toxicities (DLTs) in the first 6 evaluable subjects and 3 in the first 9 evaluable subjects. In the event of a DLT for a given subject, doses will be discontinued, the subject clinically evaluated, and taken off study. The study will be stopped for DLT resulting in death of a subject.

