### **6.3 Early Withdrawal of Subjects**

If a subject is discontinued from the study prematurely, the Investigator must select the primary reason for discontinuation on the End of Study eCRF. In addition, every effort should be made to complete the assessments listed under the “Early Term” column on the Schedule of Events.

Subjects withdrawn from the study will be considered evaluable for statistical assessment.

A subject may be removed from the study for the following medical or administrative reasons:

- Adverse Event: If a subject experiences an adverse event that the subject finds unacceptable or that, in the judgment of the Investigator or the Medical Monitor presents an unacceptable consequence or risk to the subject, the subject may be discontinued from further participation in the study.
- Administrative Discontinuation: After consultation with the Investigator or Medical Monitor, a subject may be discontinued from the study for failure to comply with protocol requirements. All instances of noncompliance must be documented in the eCRF.
- Refusal of Assessments: If for any reason, following dosing, the subject refuses further assessment during the study, the subject shall be discontinued from the study and the reasons for refusal documented. Reasonable efforts shall be made to monitor the subject for adverse events following such discontinuation. Such efforts shall be documented.

Standard supportive therapy will be maintained for subjects withdrawn from active treatment. Every effort will be made to collect safety data from these subjects through the end of study.

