#### **8.4.2 Study Day 270 ± 14 days, 360 ± 14 days, 540 ± 14 days, and 720/Early Term ± 14 days**

These visits will include a physical exam (can be symptom-driven except at Study Day 360, in which a full physical examination is required), insulin usage, vital signs, clinical laboratories CMP, CBC w diff, HbA1c, Urine MicroAlbumin panel, CrCl (calculated), adverse events, and concomitant medications. A urine pregnancy test will be collected for females of child-bearing potential at the Study Day 720/Early Term visit only.

Samples for the potency assay will be collected, and samples for pancreatic  $\beta$ -cell function will be collected.

- MMTT C-Peptide (MMTT will not be performed at the Day 270 visit, but will be collected at Day 360, 540, and 720/Early Term visits).
- Measurement of auto-antibodies, including:
  - Insulin associated aAb (IAA)
  - Insulinoma associated protein 2 (IA-2, previously known as ICA-512)
  - Glutamic acid decarboxylase (GAD65)
  - Zinc transporter 8 (ZnT8).
- Total daily insulin usage over the 3-7 days in the immediate period prior to the visit
- Any severe hypoglycemic events occurring since the prior study visit will be recorded.

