## 7.2. MISSING DATA

Missing efficacy data will not be imputed, except for missing potency assay on Visit 3/Day 1, as described in [APPENDIX 1](#).

Missing safety data will not be imputed, except for missing AE severity and relationship data (refer to [Section 17.1.1](#)). Partial or completely missing AE and medication dates will be handled as described in [APPENDIX 1](#).

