### 9.1. DISPOSITION

Number of subjects screened will be presented overall for the SCRN analysis population. Number and percentage of subjects with screen failure and reason for screen failure will also be presented overall based on the SCRN analysis population. Number of subjects randomized will be presented overall and by treatment group for the SCRN

Author:	[name]	Version Number:	2.0
Template No.:	CS_TP_BS016 Revision 6	Version Date:	23Nov2022
Effective Date:	02Dec2019	Reference:	CS_WI_BS005

analysis population.

Number and percentages of subjects treated, who completed/discontinued early from treatment (including reason for withdrawal), and who completed/discontinued early from the study (including reason for withdrawal) will be provided overall and by treatment group based on the SAF analysis population.

A listing showing inclusion and exclusion of each subject from each analysis population, including reason for exclusion, will be provided.

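### Starting a systemic immunosuppressant, or non-compliance, can end study follow-up rather than treatment alone; after one Early Term visit no later C-peptide, potency or HbA1c data are collected

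*Combined protocol and SAP*

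**What the plan says.** Protocol Amendment 3, section 8.7, on concomitant therapy: "The introduction of systemic immunosuppressive agents, however, will constitute grounds for withdrawal from the study". It sets no time limit, so it runs to Day 720. Section 6.3 adds that, after consultation, "a subject may be discontinued from the study for failure to comply with protocol requirements". Section 5.6.1 has the same pattern for a dose-limiting toxicity: "doses will be discontinued, the subject clinically evaluated, and taken off study".

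For subjects who leave early, section 6.3 asks for two things. At exit, "every effort should be made to complete the assessments listed under the “Early Term” column on the Schedule of Events". Thereafter, "Every effort will be made to collect safety data from these subjects through the end of study". It also states that withdrawn subjects count as evaluable in the statistical assessment.

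The Early Term visit shares its column in Table 3 with Days 540 and 720. It includes the MMTT (section 8.4.2: "MMTT will not be performed at the Day 270 visit, but will be collected at Day 360, 540, and 720/Early Term visits"), the potency assay, HbA1c, autoantibodies and insulin usage.

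SAP v2.0, section 9.1, tabulates subjects "who completed/discontinued early from treatment (including reason for withdrawal), and who completed/discontinued early from the study", so it treats the two as different outcomes. SAP 6.3 keeps early termination measurements out of by-visit summaries, though they are listed. SAP 6.4 applies no visit windowing. SAP 7.2 states: "Missing efficacy data will not be imputed", with an exception only for Day 1 potency. The C-peptide MMRM in SAP 16.2.2.1 uses observed cases, with visit as a factor.

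**The concern.** Treatment is short and follow-up is long. Once the third infusion has been given, a subject who starts a systemic immunosuppressant has no study treatment left to stop. Withdrawal from the study then changes only which data exist.

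Both events arise after randomisation and could be related to treatment or to the course of disease. If they are, the subjects still contributing at Months 12, 18 and 24 are a selected group. Values that were collected can be analysed with and without the period after the event. Values never collected leave no such choice.

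The documents also disagree with one another. The SAP reports end of treatment and end of study separately, but the protocol describes no route by which a subject with one of these events stays on the efficacy visits. The protocol calls withdrawn subjects evaluable, but the SAP gives their exit assessment no defined place in the by-visit analysis.

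**Working it through.** **The plan's own sample size figures.** Protocol 9.2 gives 14 AVT001 and 7 placebo subjects, a 12% event incidence and 10% dropout before Month 5.
- Chance of at least one event: 1 − 0.88^14 = 0.833, which agrees with the stated minimum of 80%.
- Dropout inflation: 21/0.9 = 23.3, rounded up to 24; by arm 14/0.9 = 15.6, giving 16, and 7/0.9 = 7.8, giving 8.

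Both reproduce and neither is in dispute.

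**Time after the last infusion.** Protocol 7.1 places infusions at Days 1, 30 and 60, the last two within 7 days either way. The latest is therefore Day 60 + 7 = Day 67.
- From Day 67: 720 − 67 = 653 days; 653/720 = 90.7%.
- From the nominal Day 60: 660/720 = 91.7%.

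**Post-baseline efficacy visits after the last infusion** (Table 3 and protocol 8.3 to 8.4):
- MMTT at Days 150, 360, 540, 720: 4 of 4.
- Potency at Days 90, 150, 270, 360, 540, 720: 6 of 6.
- HbA1c at Days 30, 60, 90, 150, 270, 360, 540, 720: 6 of 8, because the first two are taken before infusion.

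**Nominal visits missed by one withdrawn subject:**
- Leaving at Day 75: 4 MMTTs, 6 potency samples, 6 HbA1c values.
- Leaving at Day 200: 3, 4 and 4.
- Leaving at Day 400: 2, 2 and 2.

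In each case one Early Term set is sought in their place.

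**Where that set goes.** SAP 6.3 removes it from by-visit summaries, SAP 6.4 rules out mapping it to a visit by date, and SAP 7.2 rules out imputing the missed visits. SAP 16.2.2.1 needs a visit label for each observation but does not say what label, if any, an Early Term value receives.

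**Effect of one loss on precision.** Take a simple difference in means at one visit, with equal variances in the two arms and 16 v 8 subjects. The variance is proportional to 1/n1 + 1/n2.
- 16 v 8: 1/16 + 1/8 = 0.1875.
- 16 v 7: 1/16 + 1/7 = 0.2054. Ratio 1.095: variance +9.5%, standard error +4.7%.
- 15 v 8: 1/15 + 1/8 = 0.1917. Ratio 1.022: variance +2.2%, standard error +1.1%.
- 14 v 7: 1/14 + 1/7 = 0.2143. Ratio 1.143: variance +14.3%, standard error +6.9%.

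As a share of the arm, one subject is 1/8 = 12.5% on placebo and 1/16 = 6.25% on AVT001.

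**The case against.** The strongest defence has four parts.

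First, a reader might infer that these subjects' C-peptide, potency and HbA1c data are lost outright. The documents do not support that. Section 6.3 seeks a full efficacy set at exit, and values from nominal visits before withdrawal stay in the MMRM. For the same reason it would be wrong to say that the comparison is confined to subjects who stayed well and compliant. If dropout depends only on observed values, the likelihood-based model is also reasonably protected.

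Second, a reader might infer that removal is automatic. The wording is permissive: 8.7 speaks of grounds, and 6.3 says that a subject may be discontinued.

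Third, no rate is given for either event. The 10% in section 9.2 is all-cause dropout before Month 5 and is already in the sample size. Different rates by arm are possible but not shown.

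Fourth, the primary endpoints are safety, efficacy is assessed in an exploratory manner with nominal p-values, and the Month 5 analysis is complete.

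All four points stand, and they limit the size of the issue. They do not remove it. Section 6.3 also mentions subjects withdrawn from active treatment, and SAP 17.1.4 captures permanent drug discontinuation, but neither provides later efficacy visits. One Early Term set with no defined role in the model does not replace up to four scheduled MMTTs, and the assumption about dropout cannot be checked without later data.

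**Conclusion.** The concern holds in a limited form. The protocol ties these events to leaving the study, while nearly all follow-up and every post-baseline MMTT and potency sample come after the last infusion. Beyond one Early Term assessment, later efficacy data are not collected, and the SAP does not say how that assessment is used in the model.

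The size can be stated only per subject. One withdrawal costs up to four nominal MMTTs. In the placebo arm it is 12.5% of subjects and adds about 9.5% to the variance of a simple contrast (4.7% to the standard error). This assumes equal variances, 16 v 8 subjects otherwise complete, and no covariate adjustment or borrowing across visits. How many subjects are affected, and whether any bias results, cannot be determined from the documents. This is an inexpensive improvement to long-term secondary data and not a threat to the primary safety assessment.

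**What to change.** **Protocol.** Reconcile 8.7 and 6.3 with SAP 9.1 by defining end of treatment and end of study follow-up separately. Subjects with these events who still consent would stay on the efficacy and safety visits already planned. Decisions on infusions and clinical care are left as they are. Section 5.6.1 joins the two in the same way and should be read alongside them in that reconciliation.

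**SAP.** State whether and how Early Term values enter the MMRM, and make this consistent with SAP 6.3 and 6.4 and with the protocol's statement that withdrawn subjects are evaluable. Use all collected data in the main model. Add a sensitivity analysis that excludes values after the recorded start date of the immunosuppressant.

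**Cost.** A short protocol amendment and a few SAP sentences. The visits and assays are already scheduled, concomitant medications are already recorded, and the AE page already captures permanent drug discontinuation. The downside is that some retained values will be influenced by the immunosuppressant, which the sensitivity analysis addresses. SAP v2.0, section 4.2, records that the Month 5 data were locked and unblinded in 2022, so the gain is confined to the Month 12 to 24 data. Section 4.4 already foresees a SAP amendment before the final lock, and the SAP changes can go there.

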### **8.8 Immunoassessment “Potency” Assay Procedure**

“Potency” Assay will be performed by the sponsor with the subject blood sample after the AVT treatment (or placebo) to test if the function of Qa-1/HLA-E restricted CD8+ T cell is restored.

Please see “Schedule of Events” for the dates/frequency. The visit-specific blood volumes as well as specimen collection, handling, and transport procedures are described in the MOP.

“Potency” Assay will be also performed for “information only” with AVT001 made by DFCI-CMCF before applying to the subject. 2-3 vials of frozen AVT001 ( $1 \times 10^6$  cells/vial) should be sent to the sponsor for such assessment.

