## 7 Description of Study Drug

A study drug handling manual and study drug administration manual (Manual of Operating Procedures, ie, MOP) describes study drug management in detail. The MOP includes procedures for collection, transport, processing, storage, preparation (for dosing), and administration of study medication, as well as details regarding how the blinding is to be maintained during the infusion process. The following sections provide an overview of the key elements of those activities, but the MOP should be referred to for details.

Drug name and active ingredients: The study drug represents an individualized preparation of autologous immature dendritic cells, derived by culture from the subject's adherent primary monocytes with GM-CSF and IL-4 for 6 days, and loaded passively with the synthetic oligopeptide from Hsp60sp.

Formulation of dosage: AVT001 will be cryopreserved in infusible cryomedia in infusion bags. Each infusion bag will contain between  $7 \times 10^6$  and  $10 \times 10^6$  cells, and each subject randomized to AVT001 will have 3 such bags manufactured for infusion. The cryopreserved cells will be manufactured at the Dana Farber Cancer Institute Cell Manipulation Core Facility (DFCI-CMCF) and will be transported to the investigational site for infusion.

Route of administration: The infusions will be administered intravenously.

Frequency of administration: Three (3) infusions will be administered 30 (+/- 7) days apart. While there is a 7-day window for the infusions, they should occur at least 21 days apart.

Table 2 provides a summary description of the drug products, including the dosage form, the unit dose, and a physical description of the products.

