### **8.2.3 Leukapheresis**

Following randomization, all subjects (including those randomized to placebo arm as well as the AVT001 arm) will undergo leukapheresis according to standard clinical procedures.

The apheresis product will be delivered to Dana Farber Center Cancer Institute (DFCI), Cell Manipulation Core Facility (CMCF) for processing to produce AVT001. Detailed scheduling, coordination, communication, handling, and other procedures for all vein-to-vein operations are described in the MOP.

Leukapheresis is to be performed after randomization, with sufficient time for AVT001/placebo manufacture prior to the end of window between Screening Visit (Visit 1) and first infusion (Study Day 1, Visit 3). Initial manufacture of blinded IP is expected to take a minimum of 28 days.

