### 9.1 Analysis Timing and Blinding Considerations

Consistent with the study design, the primary time point for analysis is Month 5. The primary analysis for this study will be performed after the last subject has completed the Month 5 study visit, at which time the study database will be locked and the treatment allocation codes unblinded for analysis. This analysis will form the primary basis for the assessment of the study objectives.

Continuing data collection through the long-term follow-up will be performed through Month 24. While Investigators and subjects will remain blinded to the treatment allocations, assessment and analysis of outcomes will be performed by the Sponsor in an on-going manner, to better understand the longer-term effects (on both safety and efficacy) of the therapy.

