**Table 3 Schedule of Events (Protocol AVT001-T1D-01)**

Study Period	Screen/Rand/Leuk		Double-Blind Study Period (Visits 3-7)					Open-Label Study Period (Visits 8-11)		
			Double-Blind Treatment Period			Safety Assessment		Long-Term Follow-Up Period		
Study Day	$\leq -90^2$	*	1 	30 $\pm$ 7	60 $\pm$ 7	90 $\pm$ 7	150 $\pm$ 7	270 $\pm$ 7	360 $\pm$ 7	540 $\pm$ 7, 720 $\pm$ 7 / Early Term
Study Month	-3	*	-	1	2	3	5	9	12	18, 24
Visit Name	1	2	3	4	5	6	7	8	9	10, 11
Informed Consent	X									
Vein Check	X									
Randomization		X								
Medical History 	X		X							
Physical Exam 	X		X	X	X	X	X	X	X	X
Insulin Usage			X	X	X	X	X	X	X	X
Vital Signs 	X		X	X	X	X	X	X	X	X
MMTT for C-peptide			X				X		X	X
Severe Hypoglycemic Events Assessment			X	X	X	X	X	X	X	X
HbA1c and Antibody Samples	X		X	X	X	X	X	X	X	X
Laboratory Studies 	X		X	X	X	X	X	X	X	X
ECGs	X					X				
Viral Studies 	X									
Urine Pregnancy test	X		X	X	X		X			X (Day 720 /ET only)
Local tolerability of infusion site			X	X	X	X				
Leukapheresis		X 								
Potency Assay 	X (BD)	X (AVT)				X (BD)	X (BD)	X (BD)	X (BD)	X (BD)
Study Drug Administration 			X	X	X					
Adverse Events						On-going				
Prior/Commeds	Prior Meds					Commeds				

2 Screening assessments may be performed at more than 1 visit, if needed, and must be completed prior to randomization

3 At Study Day 1, a review of Medical history, symptom-driven PE, and review of eligibility should be performed prior to treatment. Details are included in note 4.

4 Medical history including prior treatment, current medicines, and drug allergies

5 Physical exam including blood pressure, pulse, temperature, weight. Can be symptom-driven physical examinations, except at Screening, Month 5, and Month 12.

6 Vital sign frequency peri-infusion is determined by site's standard of care; recommended (minimal) guidelines are provided in the MOP

7 Specified at each study visit: generally includes CMP, CBC w diff, Urine MicroAlbumin panel, CrCl (calculated); eGFR (calculated at screening only for eligibility)

8 HIV-1, HIV-2, HCV serology and HBV surface antigen

9 Leukapheresis to be performed after randomization, with sufficient time for IP/placebo manufacture prior to end of window between Screening Visit (Visit 1) and first infusion (Visit 3). Initial manufacture of blinded IP is expected to take a minimum of 28 days.

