### 4.2. PRIMARY ANALYSIS

The primary analysis had taken place for this study after the last subject completes the Month 5 study visit (SAP v1.0 was finalized on 28MAR2022 and amended via memo-to-file on 22APR2022). Data used of the primary analysis was extracted and locked 29APR2022 04:04, except the potency assay. Unblinding was performed on 17MAY2022, after the transfer of potency assay data from Avotres had been completed. All analyses described in SAP v1.0 and the binding amendment plan were produced and delivered to the sponsor on 10JUN2022. This analysis formed the primary basis for the assessment of the study objectives.

All planned analyses identified in the SAP had been performed by IQVIA Biotech Biostatistics following Sponsor Authorization of this SAP, Sponsor authorization of the analysis sets, database lock (DBL), and general study unblinding.

Author:	[name]	Version Number:	2.0
Template No.:	CS_TP_BS016 Revision 6	Version Date:	23Nov2022
Effective Date:	02Dec2019	Reference:	CS_WI_BS005

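### The sponsor reads the potency endpoint and is unblinded from Month 5 while samples continue to Day 720, with no stated safeguard; pre-dose product vials are a possible, unproven earlier route to allocation

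*Combined protocol and SAP*

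**What the plan says.** **Who reads the endpoint.** Protocol Amendment 3, Section 8.8: "Assay will be performed by the sponsor with the subject blood sample after the AVT treatment (or placebo", to test whether regulatory function is restored. Section 5.7 lists this assay as secondary endpoint (a).

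**What else the sponsor receives.** Section 8.8 adds a run for information only "with AVT001 made by DFCI-CMCF before applying to the subject. 2-3 vials of frozen AVT001", which are sent to the sponsor.

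**For whom product is made.** Section 7: "each subject randomized to AVT001 will have 3 such bags manufactured for infusion". Table 2 describes placebo as saline with DMSO in albumin, without cells. Section 8.2.3 sets the order: "Following randomization, all subjects (including those randomized to placebo arm as well as the AVT001 arm) will undergo leukapheresis". It then sends the apheresis product to the "Cell Manipulation Core Facility (CMCF) for processing to produce AVT001".

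**Who stays blinded.** Section 9.1 unblinds the allocation codes for the Month 5 analysis. After that it keeps investigators and subjects blinded, while "assessment and analysis of outcomes will be performed by the Sponsor in an on-going manner". Table 3 heads the later visits "Open-Label Study Period (Visits 8-11" and continues potency blood draws through Day 720.

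**What happened at Month 5.** SAP v2.0, Section 4.2: "Unblinding was performed on 17MAY2022, after the transfer of potency assay data from Avotres had been completed". Section 4.3 confirms that the Day 360 analysis follows an unblinding already carried out.

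**The concern.** The potency assay is the listed endpoint that directly measures in vivo reconstitution of the CD8+ regulatory system, the first secondary objective. Section 9.8.1 describes the read-out as maximum suppression before versus after treatment. The product's developer produces the result and, under SAP v2.0 Section 3.3, also evaluates it internally and reports it separately. If the reader can know the arm, a potency difference cannot be presented as an assessor-blinded finding, even though the trial is titled double-blind.

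The effect would not stop at the potency result:

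- SAP v2.0 Sections 16.2.2.1 to 16.2.2.4 enter potency as a model term in the MMRMs for C-peptide AUC, HbA1c, insulin per weight and the four autoantibodies. It is subject to backward selection there. One exploratory Day 360 C-peptide model fits all terms without selection.
- Section 5.3 makes a post-baseline potency assessment the condition for entering the PD population, on which those models are run. Section 5.4 has the sponsor authorise exclusions before lock. At the Day 360 lock that sponsor is already unblinded.

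**Working it through.** The plan gives no figure on this point, so the check sets the texts side by side and counts visits.

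**Step 1: count the potency draws.** Table 3 marks post-dose blood draws at Days 90, 150, 270, 360, 540 and 720, which is 6. Days 90 and 150 (2 draws) fall up to and including the Month 5 analysis point. Days 270, 360, 540 and 720 (4 draws) fall in Visits 8 to 11. 2 + 4 = 6.

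**Step 2: draws after unblinding.** Section 8.8 names the sponsor as reader. Section 9.1 leaves the sponsor out of those who stay blinded after Month 5. SAP v2.0 dates the unblinding to 17MAY2022. No section separates the assay readers from the rest of the sponsor or codes the samples. A sample read after 17MAY2022 is thus read by a party with access to allocation.

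**Step 3: how many draws that covers.** This depends on the enrolment date.

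- *Last-enrolled subject.* The nominal gap from Day 150 to Day 270 is 270 − 150 = 120 days. Section 8.4 allows ±7 days at Day 150 and ±14 at Day 270 (Table 3 gives ±7), so the shortest gap within windows is 120 − 7 − 14 = 99 days. If that subject's Month 5 visit took place less than 99 days before 17MAY2022, all four later draws come after unblinding. The visit date is not in the documents, so this is an assumption.
- *Early-enrolled subjects.* Some or all of the later samples may have been read before 17MAY2022.

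The exposure is therefore at most 4 of 6 time points per subject, and fewer for early enrolment.

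**Step 4: draws before unblinding.** The vials could reveal the arm if vials are sent only for AVT001 subjects and the laboratory can link a vial to a subject.

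| Text | Points towards a route to allocation | Points away |
|---|---|---|
| Section 7 | Infusion bags are made for subjects randomised to AVT001 | It restricts the bags; the test vials in 8.8 are separate containers |
| Section 8.2.3 | Randomisation comes first, so the arm is fixed before manufacture | Both arms are leukapheresed, and product goes for processing with no arm restriction |
| Table 3, Visit 2 | Product assay is scheduled before dosing | The AVT mark carries no arm restriction |
| SAP v2.0, 4.2 | Potency data were excepted from the 29APR2022 lock | They were transferred before unblinding on 17MAY2022 |

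Neither condition is stated and neither is excluded. The only blinding procedure described, in Section 7, concerns the infusion.

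**Step 5: size.** The documents give no assay variability and no reader-agreement data. The size of a reading bias cannot be calculated.

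**The case against.** The strongest reply has three parts.

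**Much of the detail sits in a manual not included here.** Section 8.8 refers specimen collection, handling and transport to the MOP, and Section 8.2.3 does the same for vein-to-vein operations. Sample coding could be described there. This stands as a limit: what can be said is that the protocol and SAP state no safeguard, not that none existed.

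**The primary time point had formal protection.** Month 5 is the primary analysis point, and the sponsor had handed over its potency data before the codes were opened. SAP v2.0 Section 4.1 places the randomisation schedule with the CRO's unblinded statistician. This also stands. A reader might infer from the vials that allocation was known for all of about 24 subjects before Day 1 (16 with vials, 8 without), and so that all six time points were read unblinded. The documents do not support this. They restrict the bags, not the vials, to the AVT001 arm, and say nothing about vial labelling.

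**The endpoint is exploratory and the later openness is disclosed.** The primary endpoints are safety. Section 5.7 has pharmacodynamic effects assessed in an exploratory manner, and SAP Section 3.3 calls potency exploratory. This lowers the severity but does not remove the point: Sections 5.7 and 2.2 still list potency as secondary, and it enters the other efficacy models. Disclosing that the sponsor analyses data after Month 5 is also different from having an unblinded sponsor generate the data.

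A reader might also suppose particular mechanisms, such as selective repeats or rejected runs. The documents do not describe the assay in enough detail to support any one of them.

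**Conclusion.** The point holds in two parts of unequal strength.

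1. **Explicit in the plan:** potency samples read after 17MAY2022 are read by an unblinded party with no stated safeguard. This covers up to four of the six post-dose time points. It covers all four for the last-enrolled subject, on the assumption about the Month 5 visit date given above.
2. **Possible but not proven:** vials sent before dosing could have revealed the arm ahead of the Day 90 and Day 150 reads. This rests on two unstated conditions, that no vials come from placebo subjects and that vials can be linked to subjects.

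The documents do not show that the Month 5 potency result was unblinded, and it should not be described that way. No sample-size or power figure changes. The safeguard should be added because it is cheap and protects a secondary endpoint and a model term. It does not bear on the primary safety conclusions and is not a condition for the trial to be interpretable.

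**What to change.** **Protocol Section 8.8.** State that all remaining blood-draw potency samples reach the sponsor laboratory under random accession numbers that show neither subject nor arm. The CRO holds the key. Each result is locked on transfer to the CRO before it is decoded, and the before-and-after comparison is made from the decoded data.

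**CSR and the final-analysis SAP amendment** (which SAP v2.0 Section 4.4 still plans before the corresponding lock). Label potency results read after 17MAY2022 without coding as not assessor-blinded. State whether the readers could link product vials to subjects when the Day 90 and Day 150 samples were read. If the MOP already described coding or reader separation, cite it there.

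Holding back the product vials would achieve little now, because the last subject had completed Month 5, and so the dosing visits, before the primary analysis.

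**Cost.** Minor relabelling and key-holding work. No visit, sample or sample-size change is needed.
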